10.4 Interim analysis

Interim analysis is not applicable; activation of the stopping rule can be any moment throughout the study period.

11. ETHICAL CONSIDERATIONS

11.1 Regulation statement

The study will be conducted according to the principles of the Declaration of Helsinki (version 10, October 2013, see for the most recent version: www.wma.net) and in accordance with the Medical Research Involving Human Subjects Act (WMO) and other guidelines, regulations and Acts.

11.2 Recruitment and consent

Patients will receive written and oral information on the study, by the treating gynaecologist. Written informed consent has to be obtained. Patients will have the opportunity to withdraw from the study at any time, will get at least a week to consider their participation in the study and will be notified in the patients' information sheet of the fact that they will have the opportunity to consult an independent physician, who is not involved in the study, for information and advice.

11.3 Objection by minors or incapacitated subjects

Not applicable.

11.4 Benefits and risks assessment, group relatedness

A full IFL is still the preferred treatment of recurrent vulvar cancer, but no comparison is made with SLN biopsy. However in breast cancer, repeat SLN is feasible and provides reliable results(12). There are no arguments why vulvar cancer should have different outcomes than breast cancer. It is possible that a SLN might increase the number of women with groin failure, opposed to standard IFL. However in our retrospective study, in 2 out of 27 patients, the SLN was located outside the surgical margins of the normal IFL, possibly due to an aberrant drainage pattern(11). So, the women with an aberrant pattern might benefit of the SLN procedure in case a positive SLN is found. Ultra-staging of the retrieved SLN might detect microscopic metastases that might have been unnoticed in IFL, and thereby improve the diagnostic (and may be clinical) outcome of affected women.

Since the majority of patients with recurrent vulvar cancer are frail, an observational study of accuracy, in which a SLN biopsy and an IFL are performed consecutively in one surgical procedure is not feasible: too many frail women will refuse this extensive surgery.

Since it is not guaranteed that a repeat SLN procedure is as safe as a primary SLN procedure, we have a stopping rule and a Safety Committee installed.

11.5 Compensation for injury

The sponsor/investigator has a liability insurance which is in accordance with article 7 of the WMO.

The sponsor (also) has an insurance which is in accordance with the legal requirements in the Netherlands (Article 7 WMO). This insurance provides cover for damage to research subjects through injury or death caused by the study.

The insurance applies to the damage that becomes apparent during the study or within 4 years after the end of the study.

11.6 Incentives

Not applicable.

12. ADMINISTRATIVE ASPECTS, MONITORING AND PUBLICATION

12.1 Handling and storage of data and documents

The Central Datacentre is organized at the Erasmus MC and consists mainly of a study coordinator and research nurse. When the patient has signed the informed consent form, the treating physician will contact the Central Registration Centre for registration of this patient. (see appendix 2 for extensive details) The registration checklist should be filled out. After verifying that the patient meets all eligibility criteria and has signed the informed consent form, the patient can be registered. Each patient will be given a unique trial number. For privacy purposes, the patient will be registered by trial number. All further documents will be coded with this CRF number, making it impossible to directly relate data to individuals. The investigator must assure that the subject's anonymity will be maintained on all documents submitted to the Central Datacentre. To enable peer review and/or inspections from Health Authorities, the investigator must agree to keep records, including the identity of all participating subjects (sufficient information to link records, e.g. CRFs and hospital records), all original signed Informed Consent Forms, copies of all CRFs. To comply with international regulations, the investigator should retain the records for 15 years after study closure. The handling of personal data will comply with the General Data Protection Regulation (GDPR).

After written approval of the participant, the data and/or body tissues will be stored for a period of 20 years after study closure for future research purposes.

12.2 Monitoring and Quality Assurance

The Central Datacentre will perform extensive consistency checks on the CRFs and returned questionnaires in case of inconsistent data that will be sent to the investigator.

A study initiation meeting to fully inform the investigator of his/her responsibilities and the procedures for assuring adequate and correct documentation will be organized by the Study Coordinators.

The decision to perform monitoring visits on-site lies with the Study Coordinators, who may also decide who will perform the monitoring visits. Initial monitoring on informed consent, eligibility and safety will be performed by the study coordinator. All records will be maintained in accordance with local regulations and in a manner that ensures security and confidentiality.

Each subject will be identified in the CRF by a subject identification number. The subject identification number will be a sequential number.

Monitoring of data will be performed as described in Appendix B of the standard Erasmus MC monitoring plan.

12.3 Amendments

Amendments are changes made to the research after a favourable opinion by the accredited METC has been given. All amendments will be notified to the METC that gave a favourable opinion.

12.4 Annual progress report

The sponsor/investigator will submit a summary of the progress of the trial to the accredited METC once a year. Information will be provided on the date of inclusion of the first subject, numbers of subjects included and numbers of subjects that have completed the trial, serious adverse events/ serious adverse reactions, other problems, and amendments.

12.5 Temporary halt and (prematurely) end of study report

The end of the study is reached when 125 patients have been successfully treated with a SLN procedure and completed two years of follow up, or earlier when the lower of upper border of the stopping rule are passed. The investigator/sponsor will notify the accredited METC of the end of the study within a period of 8 weeks. The end of the study is defined as the last patient's last visit.

The sponsor will notify the METC immediately of a temporary halt of the study, including the reason of such an action.

In case the study is ended prematurely, the sponsor will notify the accredited METC within 15 days, including the reasons for the premature termination.

Within one year after the end of the study, the investigator/sponsor will submit a final study report with the results of the study, including any publications/abstracts of the study, to the accredited METC.

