4.4 Sample size calculation

Approximately 18% of women will have groin metastases at the moment of their first vulvar cancer recurrence. Of these, approximately 20% will be detected prior to surgery (based on imaging and FNA) and these women will not be offered a SLN procedure, but advised to undergo an IFL(s). They will be asked for the observational arm of the non SLN cohort. (See figure 2)

The remaining patients will be informed about the study, they can decide on standard IFL (group A) or refuse any surgery of the groin(s) (group C) In 75% of cases that undergo SLN (group B) it will be possible to retrieve the SLN. In approximately 14,5% of women undergoing a SLN procedure a tumour positive node will be present. It is not expected that the change of a successful SLN procedure relates to the presence or absence of a positive groin node. We expect to find a positive SLN in 11% of cases undergoing a SLN procedure, a negative SLN in 64%, and an unsuccessful procedure in 25%. This corresponds to respectively 10.5%, 61.8% and 24.1% of all included patients.

Percentage failure of SLN or IFL is known for neither procedure in the recurrent setting. In the primary setting groin recurrence after negative IFL and after negative SLN are both about 3%.

Sample size for V2SLN is calculated based on a conservatively estimated groin recurrence rate of 3%, with a maximum additional groin failure rate of SLN in local recurrent vulvar SCC of 5%. The sample size, considering an alpha of 0.10 and a beta of 0.20, is then calculated to be 150 patients with a first vulvar cancer recurrence undergoing a SLN procedure (group B) and a negative SLN (Figure 2) So, we expect that approximately 243 women with a 1st recurrence of vulvar cancer should be included in the study. Stopping rules with dynamic boundaries were constructed to guarantee the safety of the study by continuously monitoring the number of groin recurrences. See Appendix 1 for a detailed description of these stopping rules.

[figure not shown]

Figure 2 Flow diagram of calculation of sample size

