Appendix 1: Stopping rules

The predictive probability design for phase II cancer clinical trial as described by Lee and Liu was used to develop the stopping rule for this study. (20) This method has the advantage over two and three stage designs that the safety can be monitored constantly rather than at a pre-specified fixed number of patients.

Under the hypothesis testing framework, this clinical trial is designed to test

$$H_0 : p \leq p_0$$

against

$$H_1 : p \geq p_1$$

where p represents the success rate of the SLN procedure, so that $1 - p$ is the failure rate. p_1 is the target success rate and p_0 is the minimally acceptable success rate. We consider a failure rate of SLN of 8% (i.e. $1 - p_1$) to be maximally acceptable, and our target failure rate (i.e. $1 - p_0$) is 3%. The study is designed such that $P(\text{Accept New Treatment}|H_0) \leq \alpha$, and $P(\text{Reject New Treatment}|H_1) \leq \beta$, where the maximum type I error α and the maximum type II error rate β are both set to 0.10.

In this model, we calculate PP continuously after 10 patients (i.e., with cohort size of 1) to monitor the treatment safety.

The stopping rule is based on the predictive probability (PP) of concluding a positive result by the end of the trial based on the cumulative information in the current stage. In this model, we calculate PP continuously after 10 patients (i.e., with cohort size of 1) to monitor the treatment safety. The trial is stopped when the PP drops below the lower bound ϑ_l , where ϑ_l is a parameter that is optimized by the method. The method of Lee and Liu also includes an option for early stopping of the trial in case the PP is very close to 1, using an upper bound ϑ_u . However, we did not utilize this option, since we do not expect to have to stop the trial in case the SLN procedure has a lower groin failure rate than IFL.

In the Bayesian predictive probability approach, we assume that the failure rate ($1 - p$) has a prior distribution of Beta (0.2; 0.8), which has a prior mean of 20%. Using the software of Lee and Liu (see

<https://biostatistics.mdanderson.org/SoftwareDownload/SingleSoftware/Index/84>) we calculated the minimum number of patients to obtain sufficient power with acceptable type I error rate using a 'max power' approach. The results gave a sample size of 150 patients, with

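### Section 12.5 ends the study at 125 successfully treated women, but the design and its error rates are for 150 women with a negative SLN, and no decision rule is given for 125

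*Protocol*

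**What the plan says.** Section 12.5 sets the end of the study: "The end of the study is reached when 125 patients have been successfully treated with a SLN procedure" and have completed two years of follow-up, "or earlier when the lower of upper border of the stopping rule are passed".

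Section 4.4 sets a different number and a different unit. It states: "The sample size, considering an alpha of 0.10 and a beta of 0.20, is then calculated to be 150 patients", and these are women "undergoing a SLN procedure (group B) and a negative SLN". Dividing by the expected share of SLN-negative women gives the inclusion target: "So, we expect that approximately 243 women with a 1st recurrence of vulvar cancer should be included in the study".

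Appendix 1 runs the predictive probability design with a maximum of 150. The unacceptable failure rate is 8% and the target failure rate is 3%. The maximum type I and type II error rates "are both set to 0.10", whereas section 4.4 has a beta of 0.20. The only active boundary is the one for too many groin recurrences. On stopping early for success the appendix says: "However, we did not utilize this option, since we do not expect to have to stop the trial"; the program input has the upper threshold at 1.0.

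**The concern.** The number that ends the study should be the number for which the error rates were calculated. Here the end rule has a smaller number and a looser unit. Section 10.2 divides women with tumour-positive SLNs by women with a successful SLN procedure, so in the protocol's own usage a successful procedure can have a positive node. The primary endpoint concerns only women with a negative SLN.

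A study closed under section 12.5 would stop short of the one analysis whose error rates are known. The primary objective is safety, and the protocol's summary puts mortality after a groin recurrence at probably 80 to 90%. Wrongly accepting a failure rate of 8% is therefore the error that the design most needs to limit.

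The reference to two borders adds to the problem. Section 9.3 calls the limit for too many recurrences the upper boundary. Appendix 1 stops when the predictive probability falls below a lower bound. These are one boundary named on opposite scales. Any second border would have to be the success bound that was left out.

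**Working it through.** **Inputs.** From Appendix 1: p0 = 0.92 and p1 = 0.97 (success), prior Beta(0.8, 0.2) on success, θ_L = 0.001, θ_T between 0.91 and 0.95, monitoring after every patient from n = 10, maximum 150. (The appendix text swaps the labels 1 − p0 and 1 − p1; the program input is correct.) From section 4.4: 11% of SLN procedures positive, 64% negative, 25% unsuccessful.

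**Step 1: reproduce the printed design.** After x successes in n women, the number of future successes Y among the remaining 150 − n is beta-binomial with parameters 0.8 + x and 0.2 + n − x. Final acceptance needs P(p > 0.92 | data) ≥ θ_T, which at n = 150 means at least 143 successes, that is, 7 or fewer recurrences. The study stops when P(x + Y ≥ 143) < 0.001. With θ_T = 0.93 this gives the printed boundary at every n from 10 to 150; from n = 60 on, the study stops at 8 recurrences. Exact recursion through the boundary gives alpha 0.0805, power 0.9160 and E(N | p0) = 93.48, all as printed. A fixed-sample check agrees: P(Bin(150, 0.08) ≤ 7) = 0.0806 and P(Bin(150, 0.03) ≤ 7) = 0.9166.

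**Step 2: women with a negative SLN at the section 12.5 end point.** If 125 means SLN-negative women, n = 125. If it means successful procedures including positive ones, n = 125 × 64/75 = 106.7, about 107.

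**Step 3: probability of not having crossed the printed boundary.** The values under 8% also stand in the last column of Appendix 1's null-case table.

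| SLN-negative women | True failure 8% | True failure 3% |
|---|---|---|
| 107 | 0.3655 | 0.9833 |
| 125 | 0.2079 | 0.9639 |
| 150 (design) | 0.0805 | 0.9160 |

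Without the interim looks, P(Bin(125, 0.08) ≤ 7) = 0.209 and P(Bin(107, 0.08) ≤ 7) = 0.369.

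**Step 4: what the table says at those rows.** A positive conclusion needs 126 successes at n = 125 and 108 at n = 107. Both exceed n, so acceptance cannot occur there. The printed probability of a positive conclusion is 0.0000 in every row before 150.

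**Step 5: could a new cut-off at 125 serve?** Fixed-sample values are shown; the interim looks change them by less than 0.001.

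| Accept at | Alpha (8%) | Power (3%) | Beta = 1 − power |
|---|---|---|---|
| ≤ 4 | 0.025 | 0.678 | 0.322 |
| ≤ 5 | 0.059 | 0.826 | 0.174 |
| ≤ 6 | 0.120 | 0.917 | 0.083 |
| ≤ 7 | 0.209 | 0.965 | 0.035 |

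No row keeps both alpha and beta within Appendix 1's 0.10. The row ≤ 5 does satisfy section 4.4's alpha of 0.10 and beta of 0.20.

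**The case against.** A reader might infer that the printed cut-off would declare an 8% failure rate safe in 21 to 37% of trials. The documents do not support that. Appendix 1 labels the rows before 150 as continuing and allows no acceptance there, and section 12.5 states no decision rule. The probabilities are the chance of arriving at that point without having stopped. They become a false acceptance rate only if the limit of 7 is carried over to the smaller number. The 0.37 also needs the section 10.2 sense of a successful procedure and the 64:11 split; the 0.21 needs neither.

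A reader might also infer that 125 cannot work at all. That is true against Appendix 1's beta of 0.10 but not against section 4.4's 0.20. The protocol holds both values, so the stronger statement fails.

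Third, the analysis set need not be exactly 125. Section 12.5 counts women who have finished two years, so with staggered entry more will have been treated by then, and the same section also defines the end as the last patient's last visit. Or 125 may be meant as completers out of 150. Either is possible, but nothing in the protocol says so, and neither supplies a rule for 125.

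Finally, the two borders do not prove that an early-success stop was intended. The wording may only mix the two scales, and Figure 3, which draws the rule, is not available here.

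What stands is the conflict in number and unit, the missing rule for 125, the conflict in beta, and an undefined second border.

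**Conclusion.** The point holds as an internal contradiction in a rule that the trial relies on, and it should be corrected before that rule is used. Only 150 SLN-negative women have a stated cut-off, alpha and power. For 125 there is none.

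The size is conditional. Under a true 8% failure rate, and if the limit of fewer than 8 recurrences were applied at the section 12.5 end point, the chance of going unstopped is 0.21 at 125 SLN-negative women. It is about 0.37 at roughly 107, the count expected if SLN-positive women are included. The design value is 0.08 and the stated maximum is 0.10. Choosing a new cut-off at 125 meets section 4.4's beta but not Appendix 1's, so the two beta values must be settled first.

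**What to change.** - **Section 12.5, number and unit.** State that the end is reached when 150 group B women with a retrieved, tumour-negative SLN have been followed for two years, the follow-up that the section already requires.
- **Section 12.5, border.** Replace the mention of two borders by the Appendix 1 boundary for too many groin recurrences. Deleting the lower border alone would not do: in Appendix 1's terms the upper bound that remains is the unused success bound.
- **Beta.** State one value in section 4.4 and Appendix 1. The printed output (beta 0.0840) satisfies either.
- **If 125 is intended.** Rerun Appendix 1 with a maximum of 125 SLN-negative women and restate the cut-off, alpha and power. The inclusion figure in section 4.4 would then change too (125/0.618 = about 202).

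The cost of the first three is a short text amendment, with the planned 150 and 243 unchanged. A requirement that 24-month groin status be known for each of the 150 should not be slipped in. Women who die, are lost, or are censored at a further vulvar recurrence would then not count, so more than 150 SLN-negative women and more than 243 inclusions would be needed. If completing two years of follow-up is meant that strictly, the protocol should say so and adjust the inclusion figure.

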2. OBJECTIVES

Primary Objective:

To investigate the safety of replacing complete IFL by SLN procedure in women with a first recurrent vulvar SCC in tumours < 4 cm.

Secondary Objectives:

- 1) To investigate the feasibility of the SLN procedure in patients with a first recurrence of vulvar SCC. (Success rate of the SLN procedure, surgical drawbacks)
- 2) To evaluate the short and long-term morbidity associated with the sentinel lymph node procedure in patients with a first recurrence of vulvar SCC.(complications, wound healing problems, long term sequela, quality of life)
- 3) To evaluate the short and long-term morbidity associated with treatment of a first recurrence of vulvar SCC.(complications, wound healing problems, long term sequela, quality of life)

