8.7 Premature termination of the study

The study will be terminated when the stopping rule is activated because of too many groin recurrences. See 4.4. sample size calculation for the stopping rules.

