9.3 Annual safety report

Groin recurrences and death of disease will be closely monitored. Safety reviews will be presented confidentially to the principal investigators every year. These annual reviews will include data on SAEs, number of deaths and cause of death, and number of groin recurrences. When the upper boundary of the stopping rule is passed all principal investigators will be informed immediately, and patient recruitment will instantaneously be paused. After interim safety analyses by the Safety Committee (see below) the study will be stopped, or continued, with or without adaptations.

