9.5 Safety Committee

An independent Safety Committee will be appointed in case the stopping rule is activated to decide to definitively stop, or continue the study.

The Safety Committee will consist of an independent gynaecologic oncologist, an oncologic surgeon, an epidemiologist, (all three with experience in clinical trials and not entering patients in the study), a lay-person representing patients, and an independent biostatistician.

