10.1 Primary study parameter(s)

Groin recurrence after SLN

The main study endpoint is the number of women who develop a groin recurrence within 24 months after a technically successful SLN procedure in which the SLN was free from tumour in recurrent vulvar cancer. The prognosis (survival) is related to failure, whether uni- or bilateral, therefore the primary endpoint relates to patients rather than groins.

Women should have a full groin node dissection in case of technical problems (SLN does not appear on the scintigraphy, or cannot be retrieved at surgery). So to calculate SLN failure the women with a groin failure after IFL will not be considered as failure of the SLN procedure.

Women that refuse to consent for standard treatment, i.e., an IFL when the SLN is not feasible (Group B2) will only be included in the analyses of the primary outcome if the SLN is retrieved.

This failure is calculated by:

Total number of women with groin recurrence in a groin after tumour-negative SLN procedure divided by the number of women with successful uni- or bilateral SLN procedure * 100%.

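### Sections 8.7 and 12.5 end the study when the stopping boundary is passed, against 9.3, 9.5 and the last-visit definition, and nothing secures 24-month follow-up after a stop

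*Protocol*

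**What the plan says.** Two sections of the protocol tie the end of the study to the boundary.

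- Section 12.5 gives a normal end, which requires completed two-year follow-up, and an alternative: "or earlier when the lower of upper border of the stopping rule are passed". The alternative carries no follow-up condition.
- Section 8.7: "The study will be terminated when the stopping rule is activated because of too many groin recurrences".

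Three other statements differ.

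- Section 9.3 says that when the boundary is passed "patient recruitment will instantaneously be paused", and that after a safety analysis "the study will be stopped, or continued, with or without adaptations".
- Section 9.5: "An independent Safety Committee will be appointed in case the stopping rule is activated to decide to definitively stop, or continue the study".
- Section 12.5, a little further on: "The end of the study is defined as the last patient's last visit".

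The primary endpoint in section 10.1 is the "number of women who develop a groin recurrence within 24 months after a technically successful SLN procedure". It is reported as a crude percentage, with no allowance for incomplete follow-up. Secondary objective 3 in section 2 is broader than the SLN procedure: "To evaluate the short and long-term morbidity associated with treatment of a first recurrence of vulvar SCC".

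**The concern.** A boundary crossing is a decision point about the SLN procedure. On that day many women will have been operated on less than 24 months earlier, so their primary outcome is not yet known. If the study ends then, the crude rate in 10.1 keeps these women in the denominator while their later recurrences are missing from the numerator, and it is biased downwards. This would happen in the situation for which the rule was built.

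The end-of-study date also has practical consequences in the protocol.

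- Section 9.4 requires SAE reporting only until the end of the study, and 9.2.2 handles groin recurrence as a reportable SAE.
- Section 12.5 asks for the final report within one year of the end. A woman operated on less than 12 months before the crossing cannot have reached 24 months by then (24 − 12 = 12).
- The groin ultrasounds at 6 and 12 months are done for the study (section 3), so routine care does not necessarily replace them.

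**Working it through.** **1. The plan's own figures.** The Appendix 1 output gives these stopping numbers of recurrences: 4 for n = 10–14, 5 for 15–24, 6 for 25–39, 7 for 40–59, and 8 for 60–150. An exact binomial recursion over these boundaries gives:

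| | True failure 8% | True failure 3% |
|---|---|---|
| Probability of a negative result | 0.9195 | 0.0840 |
| Of which before n = 150 | 0.9162 | 0.0816 |
| Probability of a positive result | 0.0805 | 0.9160 |
| Expected n | 93.4786 | 147.7381 |

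All agree with the printed output. It treats each outcome as known at once, so it says nothing about women still under follow-up at a crossing.

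**2. Inputs for the follow-up question.**

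- From the protocol: the boundaries above, a maximum of 150 SLN-negative women, the 24-month window, and the 8% failure rate.
- Assumed, because the protocol does not give them: random (Poisson) entry of 20, 30 or 40 SLN-negative women per year, and time to recurrence of 24·U months (median 12) or 24·U^1.7 months (median about 7), with U uniform on 0 to 1.
- The boundary is read against SLN-negative women operated on so far, as the caption of Figure 3 suggests. The same women form the denominator.

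**3. Definitions.** Let a crossing occur at time t with n women operated on and k recurrences seen.

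- Without 24-month status: women with no recurrence by t who were operated on less than 24 months before t.
- Missed: recurrences in these n women after t but within their 24 months.
- Crude rate = k/n. Completed rate = (k + missed)/n.

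**4. Hand check.** The women within 24 months of surgery number about 2 × yearly accrual: 40, 60 or 80. The count without status should lie somewhat below this, because some have already recurred and accrual may already have reached 150.

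**5. Results at a true rate of 8%** (4,000 simulated trials per row, means over trials that cross, about 92% of them):

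| Per year | Median months to recurrence | n at crossing | Without 24-month status | Missed | Crude rate | Completed rate |
|---|---|---|---|---|---|---|
| 20 | 12 | 111 | 37 (36%) | 1.5 | 7.6% | 9.1% |
| 20 | 7 | 107 | 37 (37%) | 1.1 | 8.0% | 9.2% |
| 30 | 12 | 121 | 54 (47%) | 2.2 | 6.9% | 8.8% |
| 30 | 7 | 114 | 55 (51%) | 1.7 | 7.5% | 9.1% |
| 40 | 12 | 128 | 71 (57%) | 2.8 | 6.4% | 8.7% |
| 40 | 7 | 121 | 71 (62%) | 2.2 | 6.9% | 8.9% |

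Percentages and rates are averaged over trials, so they need not equal the ratio of the column means. Repeat runs move the rates by about 0.1 percentage point, which extends the crude range to 8.1% and the completed range to 9.3%. The completed rate exceeds 8% because trials that cross are those with more recurrences.

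**6. Sensitivity.** Even accrual of 150 women over 3, 5 or 8 years gives 31 to 71% without status and 0.9 to 3.3 missed recurrences at 8%. At a true rate of 12%, with the accrual assumptions of step 2, the crude rate averages about 8 to 11% against about 13% completed.

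**7. Effect of the correction on the design.** Continued follow-up leaves the boundary and the decision at the boundary as they are. Alpha (0.0805), power (0.916) and the maximum of 150 are unchanged, and the number of women cut off by design falls to 0.

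**The case against.** Read as a whole, the protocol does not make a crossing the automatic end. Sections 9.3 and 9.5 provide for a pause and a committee decision that may be to continue. Section 12.5 has the last-visit definition. Three-monthly visits to 24 months are regular follow-up (section 3), and neither section 5.1.8 nor the form schedule in Appendix 4 makes an exception for an early stop. This stands. It turns the point into a contradiction plus a missing statement, and makes the figures above conditional on literal closure.

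Three stronger readings that a reader might infer are not supported.

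- *That the outcomes of treated women will never be collected.* No passage halts their follow-up. The document is silent on it after a stop.
- *That the other cohorts are certainly cut off.* This rests only on the unqualified word study. Section 13.2 distinguishes the non-SLN cohort from the V2SLN study, and section 3 gives that cohort its own information and consent forms. The ambiguity is greater for groups A and C.
- *That literal closure explains why a stopped trial could report a rate at or below 8%.* The rule acts on a predictive probability below 0.001, not on an observed rate above 8%. With 8 recurrences at n ≥ 100, k/n ≤ 8/100 = 8% even with complete follow-up. From the printed table at 8% failure, (0.4518 − 0.0805)/0.9195 = 0.40 of negative results arise that way.

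The size also depends on accrual and timing assumptions that the protocol cannot confirm, hence the ranges.

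**Conclusion.** The concern holds as an internal contradiction with a gap behind it. Sections 8.7 and 12.5 end the study at the boundary, while 9.3, 9.5 and the last-visit sentence say otherwise. Even a definitive stop decided by the committee would leave open whether women already registered are followed to 24 months.

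Under literal closure at a true 8% rate, about 36 to 62% of SLN-negative women would lack 24-month status, one to three recurrences would be missed, and the crude 10.1 rate would average about 6.4 to 8.1% instead of about 9%. This rests on 20 to 40 SLN-negative women per year and recurrences spread over 24 months. The direction of the bias does not depend on the exact values, provided some recurrences come after the crossing.

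It should be corrected. At 8% failure the boundary is crossed in about 92% of trials, and the outcomes of the women exposed to the procedure are then the main safety result.

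**What to change.** 1. Reword 8.7 and the early-end clause of 12.5 to agree with 9.3, 9.5 and the last-visit definition. Passing the boundary triggers the pause and the Safety Committee's review, and the decision to stop or continue stays with the committee. In the same edit, reconcile the two borders named in 12.5 with Appendix 1, which uses no early-success bound.
2. State that a stop does not end data collection. Outcome data of every woman already registered are collected to 24 months, with SLN-negative women first, and also groups A and C and the non-SLN cohort.
3. State that the primary rate in 10.1 is calculated when the last SLN-negative woman has reached her 24-month status, and align the final-report deadline in 12.5 with this.

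The cost is amendment wording and a later final report after an early stop. The boundary, alpha, power and sample size are unaffected.
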